### **4.3. Safety Population**

The Safety Population will include all patients who received at least one dose of study drug. This population will be used to summarize the safety data. Patients will be analyzed according to their treatment received; if an error in issuing investigational product (IP) occurs and a patient receives a mix of treatments, they will be analyzed under the treatment arm with the most IP issued to the patient.

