#### 5.2 Treatments Administered

During the double-blind Treatment Period, patients are instructed to self-administer ONE dose (2 sprays total, 1 spray per each nostril) of MORNING study drug at a fixed time in the morning and ONE dose (2 sprays total, 1 spray per each nostril) of EVENING study drug at a fixed time in the evening, with a minimum period of 6 hours between the morning and evening doses. Each patient will be dispensed 2 bottles of study drug at each visit at which study drug is dispensed. The nasal spray bottle of MORNING study drug will be clearly labeled 'MORNING', and the EVENING study drug will be clearly labeled 'EVENING'.

Study drug administration should occur as follows:

Dose	Treatment	Administration
30 IU QAM / Placebo QPM	A	1 dose from 'MORNING' nasal spray bottle = 1 spray each nostril of TNX-1900 (2 sprays total)
		1 dose from 'EVENING' nasal spray bottle = 1 spray each nostril of placebo (2 sprays total)
30 IU QAM / 30 IU QPM	В	1 dose from 'MORNING' nasal spray bottle = 1 spray each nostril of TNX-1900 (2 sprays total)
		1 dose from 'EVENING' nasal spray bottle = 1 spray each nostril of TNX-1900 (2 sprays total)

Dose	Treatment	Administration
Placebo QAM / Placebo QPM	С	1 dose from 'MORNING' nasal spray bottle = 1 spray each nostril of placebo (2 sprays total)
		1 dose from 'EVENING' nasal spray bottle = 1 spray each nostril of placebo (2 sprays total)

Patients will be trained in the use of the nasal applicator prior to home use and will receive an Instructions for Use document.

Priming of each dispensed bottle should be conducted by site staff at V2, V3, and V4.

Prior to leaving the clinic at Baseline/Randomization/Visit 2, the patient will take their first dose from the Morning dose bottle regardless of time of day. Also, on the night of Visit 2, patients should administer from the Evening dose bottle the same evening at home, with a minimum period between the two doses of at least 6 hours.

At subsequent visits (V3, V4, V5), the patient should take their AM dose of study drug from their existing study drug bottle, prior to the site collecting it and dispensing new study drug bottles. Patients should be reminded to take the AM dose prior to arriving at the clinic if possible.

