# 8.3 Visits 3 (Week 4) and 4 (Week 8)

Visits 3 and 4 are similar study visits that are scheduled to be conducted after 4 weeks, and 8 weeks of treatment, respectively. The following assessments and procedures are scheduled for both of these visits in the following general order:

- Assess changes in medication history and concomitant medications
- Assess occurrence of AEs
- Conduct nasal exam cavity examination
- Obtain vital signs
- Conduct a12-Lead ECG
- Obtain clinical laboratory tests (standard blood chemistry panel and urinalysis)
- Perform urine pregnancy test (for WoCBP).
- Obtain blood sample for optional pharmacogenomics (after the separate ICF has been signed for pharmacogenomic substudy) if not drawn already at a prior visit
- Have the patient complete placebo response training.
- Administer the "Since Last Visit" version of the C-SSRS. Results of the C-SSRS should be reviewed to ensure the patient is not experiencing suicidal ideation or has had suicidal behavior that requires emergency intervention
- Have the patient complete:
  - 1. PGIC: Patient Global Impression of Change
  - 2. HADS: Hospital Anxiety and Depression Scale
  - 3. MSQ: Migraine-Specific Quality of Life Questionnaire v2.1
- Review completed diary data and diary compliance with the patient. Provide re-training.
- Assess study drug compliance and collect previously dispensed study drug and bottles
- Dispense 2 unopened nasal applicators of double-blind study drug as assigned via the IRT (one is marked "MORNING" and the other is marked "EVENING"). Prime the two study drug bottles.
- After all the assessments at each visit have been completed, the patient should be given an appointment to return to the clinic for the next scheduled visit, and be re-instructed, as necessary, in the completion of the diary, dosing instructions, and reminded to bring study drug back to the clinic at their next visit.

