# 10.3.3 Safety Population

The Safety Population will include all patients who received at least one dose of study drug. This population will be used to summarize the safety data. Patients will be analyzed according to their treatment received; if an error in issuing IP occurs and a patient receives a mix of treatments, they will be analyzed under the treatment arm with the most IP issued to the patient.

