### 10.3. Adverse Events

An adverse event (AE) is defined as any untoward medical occurrence in a patient or clinical investigation patient administered an IP that does not necessarily have a causal relationship with this treatment. An AE can therefore be any unfavorable and unintended sign (including an abnormal laboratory finding, for example), symptom, or disease temporally associated with the use of a medicinal product, whether related to the medicinal product, or not.

Pre-existing diseases or conditions will not be considered AEs unless there is an increase in the frequency or severity, or a change in the quality, of the disease or condition. Worsening of a pre-existing condition is considered an AE.

Events that occur in patients treated with placebo, or during treatment free periods of the study, are also considered AEs.

An AE is defined as treatment-emergent if the first onset or worsening is during or after the first administration of IP and not more than 30 days after the last administration of study drug. In the case of missing or partial dates, an adverse event will be considered treatment-emergent unless the available data excludes that possibility.

An AE summary table will present totals for the following:

- All treatment-emergent adverse events (TEAEs)
- TEAEs by severity
- TEAEs leading to study drug discontinuation
- TEAEs by relationship (not related, unlikely related, possibly related)
- SAEs
- AEs of Special Interest (AESIs [See below])

Summaries of incidence rates (frequencies and percentages) of individual AEs by MedDRA SOC and preferred term will be prepared. Such summaries will be displayed for all TEAEs, TEAEs by maximum severity, and TEAEs by strongest relationship to study drug.

Each patient will be counted only once within each summation level (SOC; preferred term). If a patient experiences more than one TEAE within each summation level, the TEAE with the strongest relationship or the maximum severity, as appropriate, will be included in the summaries of relationship and severity.

All AEs will be presented in a listing.

These summaries will include SAEs; additionally, they will be presented separately (see below).

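### After a dispensing error, the Safety Population rule can place a patient who took TNX-1900 in the placebo column of the safety tables

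*SAP*

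**What the plan says.** SAP 4.3 defines the population broadly: "The Safety Population will include all patients who received at least one dose of study drug". Patients are analysed by the treatment they received, with one exception. The exception applies "if an error in issuing investigational product (IP) occurs and a patient receives a mix of treatments", and then "they will be analyzed under the treatment arm with the most IP issued to the patient". Protocol 10.3.3 has the same rule: "patient receives a mix of treatments, they will be analyzed under the treatment arm with the most IP issued to the patient".

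Protocol 5.2 sets the supply pattern: "Each patient will be dispensed 2 bottles of study drug at each visit at which study drug is dispensed". The dispensing visits are V2, V3 and V4, and at the later two the instruction is "Dispense 2 unopened nasal applicators of double-blind study drug as assigned via the IRT" (Protocol 8.3).

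SAP 10.1 runs every safety analysis on this population, without formal statistics. On timing, SAP 10.3 says "An AE is defined as treatment-emergent if the first onset or worsening is during or after the first administration of IP", with a limit of 30 days after the last dose. Protocol 10.7.3 tabulates these events by treatment group, and SAP 10.3 counts each patient once per summation level. Neither document ties an event to the product in use when it began.

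**The concern.** The exception is a majority rule on product issued. It does not ask whether the patient was exposed to oxytocin. A patient who used active spray for a month can therefore sit in the group that is meant to show the event rate without the drug, and the exposure tables in SAP 10.2 would report those days under placebo.

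The placebo column carries weight in this trial. Protocol 7.2.8.1 singles out nasal irritation and events suggesting antidiuretic or blood-pressure effects. The synopsis plans no formal safety data monitoring, and no safety test is specified. The reader will judge these events by comparing columns, and an exposed patient with an event in the placebo column narrows the visible difference.

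The rule is also incomplete. It does not resolve ties, and it does not say whether the most product is counted in kits, bottles or doses.

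**Working it through.** The plan states no dispensing-error rate and no expected event rate, so there is no figure of its own to reproduce. The check applies the rule to every possible mix and then sizes the effect under stated assumptions.

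Inputs:
- Dispensings: three. "Priming of each dispensed bottle should be conducted by site staff at V2, V3, and V4" (Protocol 5.2). The two bottles from one visit are treated here as one kit.
- Treatment Period: about 84 days (Protocol 3.1), so one kit covers 84/3 = 28 days, or 28/84 = 33% of treatment.
- Patients per arm: about 100 (Protocol 10.2).
- Arms: A (active morning, placebo evening), B (active both), C (placebo both).

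**Step 1: apply the rule.** Three dispensings give 3 × 3 × 3 = 27 kit sequences. Removing the 3 unmixed ones leaves 24. A two-to-one majority for a given arm arises in 3 positions × 2 possible odd kits = 6 ways. So 6 sequences are labelled A, 6 are labelled B, 6 are labelled C, and the remaining 6 (one kit of each) are ties. The six labelled placebo are A-C-C, B-C-C, C-A-C, C-B-C, C-C-A and C-C-B. Every one contains an active kit. A patient who stops after two dispensings has 9 − 3 = 6 possible mixed sequences, all of them ties.

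**Step 2: the unit.** A patient issued A-A-C is Arm A when counted in kits. Counted in bottles, the same patient has 1 + 1 + 0 = 2 active and 1 + 1 + 2 = 4 placebo bottles, so the label depends on a choice that neither document makes.

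**Step 3: effect on the placebo column.** Let p be the true placebo event rate and k the number of exposed patients with the event in a placebo column of 100. The reported rate is (p × (100 − k) + k)/100. The values of p are assumptions.
- p = 5%, k = 1: (0.05 × 99 + 1)/100 = 5.95%
- p = 5%, k = 2: (0.05 × 98 + 2)/100 = 6.9%
- p = 2%, k = 1: (0.02 × 99 + 1)/100 = 2.98%
- p = 2%, k = 2: (0.02 × 98 + 2)/100 = 3.96%

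**Step 4: effect on a risk difference.** One patient is 1/100 = 1 percentage point of a column. Counting an exposed patient with an event under placebo instead of an active arm raises placebo by about 1 point and lowers that active arm by about 1. The contrast of that arm with placebo shifts by about 2 points. The other active arm's contrast shifts by about 1.

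**Step 5: how many patients.** Suppose, as an assumption, that 0 to 2% of 300 patients have an issuing error, which is 0 to 6 patients. Assume also one wrong kit each, all three dispensings completed, and errors spread evenly over arms. An Arm A or B patient with one wrong kit keeps a majority of the randomised kits and stays in the active arm. Only errors in placebo patients leave an exposed patient under placebo, about one third of the total: 0 to 2 patients. At a 1% rate it is 3/3 = 1 patient.

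**The case against.** The strongest reply is that this is a contingency rule which may never be used. Kits are assigned through the interactive response system, bottle numbers are recorded (Protocol 8.2), and dispensing records must identify who received each bottle (Protocol 5.9). That stands, and it is why the point is minor.

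Some mitigation exists. Deviations are classified before unblinding and listed by patient (SAP 7.1), all adverse events are listed (SAP 10.3), and nasal cavity events carry information on their timing relative to dosing (SAP 10.4). A careful reader could trace an affected patient. The summary columns, however, would not change.

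The rule also errs in the other direction: a mainly active patient's events during a placebo kit count under active treatment. A reader might infer that the rule systematically favours the drug. The documents do not support that.

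A reader might also see a contradiction between analysis by treatment received and assignment by amount issued. There is none. Treatment received has no single answer for a mixed patient, and the clause is an explicit exception. The weakness is in which exception was chosen.

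Finally, issued product is a firmer record than product taken, because SAP 7.3 captures no direct compliance measure from drug accountability and relies on diary reports. This is fair, and it is a reason to use bottle numbers and diary together.

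**Conclusion.** The point holds in a limited form. If an issuing error gives a patient one TNX-1900 kit and two placebo kits, the plan counts that patient, and any events from the TNX-1900 month, as placebo. No other section overrides this. The size is roughly 1 to 2 percentage points of risk difference per affected patient with an event, assuming about 100 per arm. The total could be zero, because the error rate is unknown and an affected patient must also have an event of interest.

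It would be tempting to conclude that a drug-related safety signal will be hidden. The documents do not support that: they give no error rate, and under the assumed 2% rate only about two exposed patients would sit under placebo. Efficacy is untouched, since the mITT population is analysed as randomised (SAP 4.2), and no test or decision rule depends on the safety columns. This is a cheap improvement to make before unblinding, and it does not threaten the trial's conclusions.

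**What to change.** In SAP 4.3 and Protocol 10.3.3, replace the exception with wording to this effect: for safety summaries, a patient who took at least one dose of TNX-1900, judged from dispensed bottle numbers and diary dosing, is analysed in an active arm, and the placebo column contains only patients never exposed. If active kits from both arms were received, the arm is the one with more active kits, counted in kits, with ties going to the higher regimen. Flag mixed-treatment patients in the adverse event listings. The text should also say whether a dispensed active bottle counts as taken when the diary is blank.

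Applied to the 24 mixed three-kit sequences, this leaves none under placebo and none unresolved. Arm A receives the 6 A-and-C mixes and the 3 with two A kits and one B, which is 9. Arm B receives the 6 B-and-C mixes, the 3 with two B kits and one A, and the 6 with one of each, which is 15. The total is 9 + 15 = 24.

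Keeping the majority rule between active arms matters. Assigning everyone to the highest regimen ever taken would move a patient with two A kits and one B kit into Arm B and blur the comparison of the two regimens.

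The cost is a wording change in two documents and some reconciliation of bottle and diary records for any affected patient. The downside is that events from a mis-dispensed patient's placebo period will count under active treatment and slightly dilute that column. No sample size or power figure changes.

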## 5. ESTIMANDS FOR PRIMARY AND KEY SECONDARY EFFICACY ENDPOINTS

### 5.1. Primary Efficacy

The primary efficacy endpoint is defined as the mean change in monthly migraine days from Baseline (last 28 days prior to randomization) to month 3 (last 28 days of treatment). For defining months, diary days will be divided into 28 day “months”; Days 1 to 28 will be Month 1; Days 29 to 56 will be Month 2; and Days 57 to 84 will be Month 3. The change in count of days with migraine vs the baseline will be compared between treatment groups.

The target population is all patients in the mITT population with CM as defined by the inclusion/exclusion criteria.

In general, a “while on treatment” policy strategy will be used for all intercurrent events. That is, the data will be considered independently from any intercurrent event, such as rescue medication usage and study discontinuation. One exception is that patients that report a headache believed to be a migraine that was resolved by a migraine-specific abortive rescue medication will be counted as a migraine (see section 9.1). The approach for partial and missing data is described in Section 9.1.1.

The population-level summary will be the model-based least-squared means for each arm and differences between treatment arms (analyzed as randomized) at month 3. The model is given in Section 9.1.2.

### 5.2. Key Secondary Efficacy

There are six key secondary efficacy endpoints. For all, the target population is all patients in the mITT population with CMs as defined by the inclusion/exclusion criteria. The key secondaries (in order) are:

- Proportion of patients experiencing a  $\geq 50\%$  reduction in the number of migraine headache days from the last 28 days of Baseline to the month 3 28-day normalized migraine headache days. The percent change from baseline will be calculated for each month as  $100 * [\text{monthly count} - \text{baseline count}] / [\text{baseline count}]$ .
  - A composite strategy will be employed to handle missing data and discontinuation. Concomitant medications and all other intercurrent events will use a treatment policy strategy; data will be analyzed as observed. For all missing data (whether or not due to discontinuation), they will be assumed to be non-responders; that is, failure to stay on-trial and provide data is assumed to reflect non-response to study treatment.
  - The population-level summary will be the percentages of responders in each arm and difference in percentages of responders between treatment arms (analyzed as randomized) at month 3. See Section 9.1.4.2 for full details

- Mean change in the number of days using rescue medication (triptan, ergot derivative, or other migraine-specific acute medication) from the last 28 days of Baseline to the last 28 days of treatment.
  - A “while on treatment” policy strategy will be used for all intercurrent events. That is, the data will be considered independently from any intercurrent event, such as study discontinuation. The approach for partial and missing data is described in Section 9.1.1 (Missing data approach will be identical to that of the primary endpoint).
  - The population-level summary will be the model-based least-squared means for each arm and differences between treatment arms (analyzed as randomized) at month 3. See Section 9.2.1.1 for details.
- Proportion of patients with a Patient Global Impression of Change (PGIC) rating of 1, “very much improved”, or 2, “much improved”, at Week 12.
  - A composite strategy will be employed to handle missing data and discontinuation. Concomitant medications and all other intercurrent events will use a treatment policy strategy; data will be analyzed as observed. For all missing data (whether or not due to discontinuation), they will be assumed to be non-responders; that is, failure to stay on-trial and provide data is assumed to reflect non-response to study treatment.
  - The population-level summary will be the percentages of responders in each arm and difference in percentages of responders between treatment arms (analyzed as randomized) at month 3. See Section 9.2.1.2 for full details
- Mean change in the number of moderate or severe headache days from the last 28 days of Baseline to the last 28 days of treatment. A moderate or severe headache day is defined as any calendar day wherein a patient records a headache or migraine of moderate or severe peak intensity in the e-diary.
  - A “while on treatment” policy strategy will be used for all intercurrent events. That is, the data will be considered independently from any intercurrent event, such as study discontinuation. The approach for partial and missing data is described in Section 9.1.1 (Missing data approach will be identical to that of the primary endpoint).
  - The population-level summary will be the model-based least-squared means for each arm and differences between treatment arms (analyzed as randomized) at month 3. See Section 9.2.1.3 for details.
- Mean change in the number of migraine headache days from the last 28 days of Baseline to average number per 28 days over the entire 12 week duration of Treatment Period.
  - A “while on treatment” policy strategy will be used for all intercurrent events. That is, the data will be considered independently from any intercurrent event, such as study discontinuation. The approach for partial and missing data is

described in Section 9.1.1 (Missing data approach will be identical to that of the primary endpoint).

- The population-level summary will be the model-based least-squared means for each arm and differences between treatment arms (analyzed as randomized) at month 3. See Section 9.1.4.1 for details.
- Mean change from Baseline in the Migraine-Specific Quality of Life Questionnaire Role Function, Restrictive domain (MSQ v2.1) at Week 12.
  - A “while on treatment” policy strategy will be used for all intercurrent events. That is, the data will be considered independently from any intercurrent event, such as study discontinuation.
  - The population-level summary will be the model-based least-squared means for each arm and differences between treatment arms (analyzed as randomized) at month 3. See Section 9.2.1.4 for details.

## **6. STUDY PATIENTS**

### **6.1. Disposition of Patients**

The number and percentage of patients in each analysis population will be summarized. The number of patients screened, patients enrolled, and the number and percentage of patients completing the study, discontinuing from the study and reasons for discontinuation will also be reported. All percentages will be calculated using the number of patients enrolled as the denominator.

### **6.2. Demographic and Other Baseline Characteristics**

Demographic and baseline characteristics such as age, gender, race/ethnicity, height, weight, BMI, family status, education, employment status, smoking history, use of preventative meds, chronic migraine history, number of baseline headache days, number of baseline migraines, and baseline diary compliance (see section 7.3) will be summarized by treatment group (TNX-1900 and placebo) and overall for the mITT and Safety populations. Categorical items will be reported with counts and percentages; continuous items will be reported using summary statistics (mean, standard deviation (SD), median, minimum, maximum).

### **6.3. Prior and Concomitant Medications**

Prior medications are defined as medications or therapies initiated prior to the start of the study drug and terminated prior to the start of study drug. Hence, these medications or therapies will have end dates prior to the first dose date of study drug. Concomitant medications are defined as any medications other than the study drug that a patient receives concurrently with the study drug. These medications will have end dates on or after the first dose date of the study drug if they have an end date. In the case of missing or partial dates, medications will be considered concomitant unless the available data excludes that possibility.

All medications will be coded using the World Health Organization Drug Dictionary (WHO-DD). Prior and concomitant medications will be summarized by treatment group and by the number and percentage of patients taking each medication, classified by using WHO-DD Anatomical Therapeutic Chemical Level 3 and preferred term.

Prior, but previously discontinued (prior to screening for the study), preventative migraine medications will be collected on a separate case report from (CRF) with additional information on the tolerability and efficacy of the medication. These will be summarized by treatment group and by the number and percentage of patients taking each medication (grouped by preferred term) as well as the number and percentage for each level of the patient reports of effectiveness and tolerability. Any preventative migraine medication used within 90 days of the Screening visit will be recorded on the Prior and Concomitant Medication CRF.

Additionally, prior other treatments or devices used within 90 days of the Screening Visit (ie. acupuncture, electrical or magnetic stimulating devices, chiropractor, PT, etc.) will be collected and tabulated by type of therapy.

All medications and therapies will be presented in listings, with prior preventative migraine medications listed separately.

